**Create or insert table to describe the exclusion criteria and methods to ascertain them**

EXCLUSION CRITERIA	METHOD OF ASCERTAINMENT
1. Meets DSM IV criteria for bipolar disorder, schizophrenia or any psychotic disorder other than transient psychosis due to drug abuse. Substance Induced Mood Disorder with Hamilton Depression Scale score $\geq 15$ will be excluded. Patients with Major Depressive Disorder will be eligible to participate, provided they are in remission (Hamilton Depression Scale-25 Score < 8), whether receiving treatment or not.	MINI interview, self-report
2. History of allergic, dermatological, or adverse event related to oxytocin or desmopressin. Patient using oxytocin or vasopressin-based products cannot participate.	Self report
3. Chronic organic mental disorder, insufficient proficiency in English, or any condition or status (illiteracy) that would render an individual incapable of giving informed consent.	Psychiatric evaluation
4. Significant current suicidal risks, suicide attempt within the past year.	Psychiatric evaluation
5. Unstable physical disorders, which might make participation hazardous: hypertension (>140/90), hepatitis (patients with chronic	Medical evaluation

mildly elevated transaminase levels (2-3 X upper limit of normal will be considered acceptable if PT/PTT is normal), serum sodium (Na) < 133 mEq/L, renal failure (creat >2; BUN > 40. History of hyponatremia. Patients on medication (\*) (see partial list below) that may induce hyponatremia will not be excluded, provided no evidence of hyponatremia is found at screening.

6. Coronary vascular disease as indicated by history, or suspected by abnormal ECG. Electrocardiogram, medical history

7. Currently meets DSM-IV criteria for another substance dependence or abuse disorder other than nicotine, or alcohol. If alcohol dependent, must not be in need of detoxification. MINI, medical eval, utox

8. Participants who cannot comply with study procedures during the inpatient or outpatient abstinence induction (phase 1) will not proceed to phase 2. Study performance

9. Pregnancy, positive urine pregnancy test, or breastfeeding. Women who wish to participate must agree to use a method of contraception during the study and sign a written commitment to that effect, and submit to a urine pregnancy test every two weeks of phase 2 History, medical monitoring.

10. History of transphenoidal surgery or sinus surgery in the past month. Simple nasal congestion is not exclusionary. History, medical screening.

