The psychiatric evaluation is conducted by a research psychiatrist (MD). It includes a psychiatric and medical review of systems, a mental status examination, a review of inclusion/exclusion criteria, and of the diagnostic evaluation. A consensus diagnosis is reached, which must include cocaine dependence, and not include any exclusion diagnoses.

The MD then conducts the medical evaluation, including: medical history, review of systems, physical examination including vital signs, olfactoscopic examination of the nasal cavity, screening blood test (chem-20, CBC, urinalysis, urine toxicology, urine pregnancy test for women patients), and an electrocardiogram. The Scent test is conducted at this point.

When completed, and the laboratory reports received, the assembled information is reviewed by the principal investigator or a research MD familiar with the study protocol. This information is reviewed against the inclusion/exclusion criteria of the study to determine eligibility to participate. For control participants, the screening process is the same as described for cocaine-dependent patients. For potential control participants entering through the STARS clinic, they will sign the

screening consent form (IRB# 4436R). Those entering through DOSA, they will sign the study consent form for control participants (Einstein IRB# pending)

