IRB# 4436R) describing the evaluation process in detail. For patients enrolling through DOSA, the screening process is included in the consent form for the study (Einstein IRB# 2014-3568). The screening process begins with completion of the following forms: locator form; demographic form, drug history questionnaire, concomitant medication form. The locator form indicates the patient's name, address, phone number, as well as names, addresses and phone numbers of family members and close friends, along with a permission to contact them. The demographic form records information about education, marital status, employment, income, social support, housing, gender and racial category. The drug history questionnaire reviews lifetime use of drugs by category, as well as any previous treatment attended. The psychiatric diagnostic evaluation follows, conducted by a member of the research staff (LCSW, CASAC, MD, PhD) trained in the administration of the Mini International Neuropsychiatric Interview (MINI; Lecrubier et al., 1997), a treatment/drug use history, and a Hamilton Depression Scale – 25 (Williams, 1988). The evaluation is conducted by a research psychiatrist (MD). It includes a psychiatric and medical review of systems, a mental status examination, a review of inclusion/exclusion criteria, and of the diagnostic evaluation. A consensus diagnosis is reached, which must include cocaine dependence, and not include any exclusion diagnoses. The MD then conducts the medical evaluation, including: medical history, review of systems, physical examination including vital signs, olfactoscopic examination of the nasal cavity, screening blood test (chem-20, CBC, urinalysis, urine toxicology, urine pregnancy test for women patients), and an electrocardiogram. The Scent test is conducted at this point. When completed, and the laboratory reports received, the assembled information is reviewed by the principal investigator or a research MD familiar with the study protocol. This information is reviewed against the inclusion/exclusion criteria of the study to determine eligibility to participate. For control participants, the screening process is the same as described for cocaine-dependent patients. For potential control participants entering through the STARS clinic, they will sign the screening consent form (IRB# 4436R). Those entering through DOSA, they will sign the study consent form for control participants (Einstein IRB# 2014-3568) 2. Informed Consent For patients from DOSA, they signed the consent form for the study at the time of screening. If the patient is found eligible to participate in the research study, they will be informed of this, and arrangements will be made with them (and with their counselor if applicable) to begin. For patients from the STARS clinic not meeting any exclusion criteria, we inform the patient about their eligibility to participate. If the patient agrees to participate, a consent appointment is set. The consent form for the study is presented to the patient to read. After reading, the patient answers a consent quiz to verify their understanding of the study they are about to begin. For control participants entering through DOSA, they will have signed the consent form written for control participants at the time of screening. For control participants entering through the STARS clinic, they will sign the consent form for control participants.

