**Type in the name(s) not found in the above list**

**Study Procedures**

**Describe the procedures required for this study**

**Design Overview:**

This is a 2 phases, 7-weeks, prospective, double-blind, placebo-controlled, randomized clinical trial of comparing intranasal oxytocin to placebo in cocaine-dependent patients. The principal aim of the study is to examine if intranasal oxytocin can reduce the relapse risk. Cocaine-dependent and control patients will be recruited through IRB-approved advertising in public media, and from the STARS clinic of the Division on Substance Abuse at the New York State Psychiatric Institute, and the Division on Substance Abuse at the Albert Einstein College of Medicine. Prior to the 6-week outpatient phase, cocaine-dependent patients will be required to become abstinent. To achieve this, patients will opt for either an inpatient or an outpatient approach. During the inpatient approach, patients will be hospitalized at the New York State Psychiatric Institute (5-South) for 7 days to establish abstinence, participate in the stress challenge over 2 separate days which evaluates baseline stress sensitivity, investigate if oxytocin can exert an acute effect on stress parameters, and begin on randomized medication (IN oxytocin 24 IU/day vs. IN placebo). There will not be a placebo lead-in.

Table 1 presents an overview of phase 1 for cocaine-dependent and control patients.

see up-loaded table 1.

---

Because of professional, personal, or financial reasons, some patients may choose *the outpatient abstinence-induction procedure*. During this week, patients will need to attend the clinic on three consecutive days and provide a negative urine toxicology for cocaine at each visit. Following this, they must complete all the study procedures prescribed in the in-patient Phase 1 procedure: essentially the stress challenges as described in section 4A3 below. If a patient cannot remain abstinent during this week, the patient will be offered another attempt to become abstinent during following week and complete the phase 1 procedures. If a patient cannot achieve abstinence during either week, then the inpatient phase will be mandatory for continued participation. If the patient cannot do this, we will offer referrals for treatment in another setting.

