**see uploaded Figure 1**

Each testing period will begin with the insertion of a saline lock. Following the saline lock insertion, there will be a 2-hour habituation interval before any testing begins. The testing will begin around noon to 1 pm, when the diurnal secretion of ACTH usually falls to allow easier detection of ACTH variation due to the experimental variations.

After habituation, baseline levels of ACTH, **BP, HR, subjective ratings of anxiety, restlessness, cravings for cocaine (Likert scales) are obtained. Research staff complete a behavioral activation scale during the endocrine challenge at those same specific time points ([name], personal communications). The patient is then asked to insufflate 40 IU (10 ug or 0.1cc) of desmopressin in each nostril.** At each of the specified time points in figure 1, repeat measurements of ACTH, BP, HR, subjective ratings, and **staff observer ratings are also obtained.** A relaxation procedure (specific muscle group tension and relaxation) used in protocol NYSPI IRB 6013, will also be used to close the day of testing. **At the next day of testing, the procedure begins by placement of a saline lock and habituation for two hours. Baseline levels of ACTH, BP, HR, subjective ratings and staff observer ratings are drawn. Then the patient is asked to insufflate 12 IU (16 ug or 0.3cc) of oxytocin in each nostril. Repeat measurements are obtained as during baseline occur at specified time points. Forty minutes later, patients insufflate 40 IU of desmopressin in each nostril, and all**

---

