**measurements are repeated at specified time points.**

5) After baseline stress testing is completed, begin randomized administration of intranasal Oxytocin 20 IU per day in the morning, for each remaining day of phase 1. This will serve also as an opportunity to train patients on how to administer intranasal solutions. The steps are as follows: 1) exhale through the nose, head bent forward; 2) while inhaling, spray once into one nostril; 3) repeat step 1 & 2 for the other nostril; 4) repeat steps 1 to 3 again to reach the daily dose of 24 IU of randomized medication. The patients will be instructed by a member of the research staff to ensure proper technique and optimal absorption of the medication. The Oxytocin solution is stable at room temperature for one month after being opened. Nonetheless, the manufacturer recommends that the bottle be kept refrigerated between uses and we will recommend this to the patients as well. Its stability should ensure that transportation to the clinic should not cause degradation, provided it is not exposed to extreme heat (> 100 Fahrenheit), direct sunlight, or frozen.

Phase 1, control participants.

The purpose of Phase 1 for control participants without psychiatric, medical, or addiction disorders is to test their stress sensitivity with the same procedure as cocaine-dependent patients. This is to study if stress dysregulation is more prevalent among cocaine users than normal controls, and to study if vasopressin-based stress mechanisms bear some specificity to the stress dysregulation observed in cocaine-dependent patients.

For control participants, the procedure will be carried out over two days as outpatients. They will be instructed to present themselves between 9 to 10 am on a testing morning, having eaten breakfast. A saline lock will be inserted, and a 2-hour habituation period will follow before testing begins at approximately 1 pm. The procedure will be the same as described for cocaine-dependent patients, and will be administered in counterbalanced order (**see above, stress procedures**). Completion of phase 1 ends their participation in this study.

Phase 1, week 1, cocaine-dependent patients, outpatient version.

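### In the visible text, nothing repeats the screening pregnancy test or limits its age before cocaine-dependent women receive Phase 1 drugs; on the slower permitted routes it can be more than two weeks old

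*Protocol*

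**What the plan says.** **When women are tested.** The screening medical evaluation (Protocol, Recruitment Procedures, repeated under Consent Procedures) includes a "urine pregnancy test for women patients". Exclusion item 9 then asks women to "submit to a urine pregnancy test every two weeks of phase 2". Phase 2 item 4 and the SAP's Phase 2 measures put those tests at weeks 2, 4 and 6. Phase 2 runs from week 2 to week 7. A positive test ends participation.

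**What is given between screening and week 2.** In the desmopressin challenge the patient is asked to "insufflate 40 IU (10 ug or 0.1cc) of desmopressin in each nostril", on two separate days. On one of those days she is first asked to "insufflate 12 IU (16 ug or 0.3cc) of oxytocin in each nostril". After the challenges, staff "begin randomized administration of intranasal Oxytocin 20 IU per day in the morning, for each remaining day of phase 1" (the same item later gives the daily dose as 24 IU).

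**What is re-checked.** The outpatient version of Phase 1 calls for a cocaine-negative urine ahead of every challenge day. No pregnancy test appears in the Phase 1 procedures for either setting.

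**Other protection.** Item 9 also states: "Women who wish to participate must agree to use a method of contraception during the study and sign a written commitment to that effect".

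**The concern.** Pregnancy is checked at entry and every two weeks once Phase 2 has begun, but the visible text has no check at first exposure. Item 9 ties repeat testing to Phase 2, so a site following it as written has no instruction to test again before the challenges.

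Time can pass after the screening test. Laboratory reports and an eligibility review follow it. For STARS patients there is a further step: "If the patient agrees to participate, a consent appointment is set". The section on delay to treatment allows up to two to three weeks of work-up in complicated cases. A woman who fails outpatient induction is not dropped: "the patient will be offered another attempt to become abstinent during following week and complete the phase 1 procedures". After a second failure she can be admitted instead.

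At stake is giving desmopressin, open oxytocin and the first randomised doses on an outdated negative result. The Protocol expects 45% women, about 0.45 × 50 = 22.5 of the 50 cocaine-dependent completers. Not all will be of childbearing potential.

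**Working it through.** The documents state no figure for the age of the test, so there is none to reproduce. The check counts elapsed calendar days from the screening test to dosing.

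**Inputs**
- g = days from the pregnancy test to the start of induction or admission. The documents do not fix it. Assumed range: 0 (test at the end of the work-up, immediate start) to 21 (test on the first day of the longest work-up). A long work-up with early testing is g = 14 to 21.
- Outpatient attempt: 7 weekdays, with at least three consecutive negative daily urines before any challenge (Protocol, Phase 1 outpatient version). The earliest challenge is therefore weekday 4. I assume the challenges fall inside the 7 weekdays.
- Second attempt: another 7 weekdays (weekdays 8 to 14 if the first is used in full), then an offer of admission (weekday 15).
- Inpatient Phase 1: 7 days (Design Overview).
- Yardstick: 14 days, borrowed from item 9.

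**Weekdays turned into elapsed days**, over Monday to Friday starts, counting the first day as 0:
- weekday 4: 3 to 5 days
- weekday 7: 8 to 10 days
- weekday 9: 10 to 12 days
- weekday 11: 14 days for every start
- weekday 14: 17 to 19 days
- weekday 15: 18 to 20 days

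**Age of the screening result**

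| Route | Formula | g = 0 | g = 14 to 21 |
|---|---|---|---|
| One outpatient attempt, earliest first challenge | g + 3 to 5 | 3–5 | 14+3 = 17 to 21+5 = 26 |
| Early failure (positive on weekday 5), restart, next challenge on weekday 9 | g + 10 to 12 | 10–12 | 24–33 |
| First period used in full, restart, earliest challenge on weekday 11 | g + 14 | 14 | 28–35 |
| Same route, last day of second period | g + 17 to 19 | 17–19 | 31–40 |
| Two failed attempts, day of admission | g + 18 to 20 | 18–20 | 32–41 |
| Direct admission, any day of the stay | g + up to 7 | up to 7 | 14–28 |

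Challenges after inpatient fallback come on or after the day of admission, so 18 to 20 is a lower figure for that route.

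**Break-even against 14 days**
- One outpatient attempt: the earliest challenge passes 14 days once g exceeds 14 − 5 = 9 to 14 − 3 = 11 days.
- Restart after a fully used first period: the earliest challenge is exactly at 14 days when g = 0. It passes 14 with any screening delay, or if the challenge falls later in the second period.
- Inpatient fallback: past 14 days at any g.

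**Sensitivity.** The outpatient section also calls the two attempts a two-week window. Read as 14 calendar days, a restart at g = 0 ends no later than day 14, and inpatient fallback begins from day 14 rather than day 18 to 20. On that reading a restart passes 14 days only if a screening delay is added.

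**The case against.** The strongest objection is that silence in the visible text does not prove absence. The Phase 1 schedule is delegated to uploaded Table 1. Uploaded Table 2, the uploaded study-assessments table and screening protocol 4436R are not available either, and the visible SAP list of Phase 1 measures starts at item 2. Table 3 is broken in extraction and cannot settle the matter. This stands. A reader might infer that no pre-dose test exists anywhere, and the documents do not support that.

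The 14-day yardstick is also borrowed. Item 9 sets a monitoring interval for Phase 2 and does not say how long an eligibility result remains valid. It serves here only as the one interval the protocol itself accepts. Exceeding it is not a breach of a stated rule.

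The slow routes are exceptions. The section on delay to treatment says the work-up is readily finished at the first screening visit, and its two-to-three-week figure is a ceiling. A reader might infer that any restarted induction makes the result too old, but an early failure and restart alone gives only 10 to 12 days.

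Finally, the written contraception commitment covers the whole study and lowers the risk. It does not remove the case for a test, since the protocol keeps two-weekly testing in Phase 2 alongside it. A reader might also infer that pregnant women will be dosed. The documents give no basis for a number, and they note that obstetric oxytocin doses far exceed those used here.

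**Conclusion.** The gap is real in the visible text and modest in size. With a quick work-up and one induction attempt, the screening result is under two weeks old at first dose and little is lost. At first challenge it can be about 17 to 26 days old after a long work-up with early testing, and about 18 to 20 days or more after inpatient fallback. It also passes two weeks after a restart that uses most of the first period or follows a screening delay. A long work-up followed by a full restart gives 28 to 35 days at the earliest challenge of the second attempt, but this combines two extremes and is not typical.

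These figures assume weekday counting of the 7-day periods, challenges held inside them, and, for the long work-up, a test at its start. How often the slow routes occur is unknown. Confidence is medium because of the schedules that cannot be seen. The change is still worth making: the text as written gives no trigger for a repeat, and the remedy costs almost nothing.

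**What to change.** In exclusion item 9, the Phase 1 procedures (inpatient and outpatient) and Table 3, require a negative urine pregnancy test on the day of the first Phase 1 challenge, before any study drug, using the urine already collected for toxicology. Repeat it if induction is restarted or moved to the inpatient unit. A positive result ends participation, as Phase 2 item 4 already provides.

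If uploaded Table 1, the study-assessments table or protocol 4436R already requires this, carry the requirement into the protocol text.

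Cost: one to three extra dipsticks per woman (one before the first challenge, one on a restart, one on a move to the ward) and a schedule amendment. No extra visit or specimen is needed.

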## Inclusion/Exclusion Criteria #2

### Name the subject group/sub sample

control sample

Create or insert table to describe the inclusion criteria and methods to ascertain them

#### INCLUSION CRITERIA

1. Age 18 to 60

#### METHOD OF ASCERTAINMENT

MINI interview,

- |   |                                     |
|---|-------------------------------------|
|   | self-report, ID confirmation        |
| 2. Able to give informed consent and comply with study procedures                   | Self-report, Psychiatric Evaluation |
| 3. Can pass the blindfolded scent test recognizing the scent of cinnamon or coffee. | Scent test                          |

**Create or insert table to describe the exclusion criteria and methods to ascertain them**

EXCLUSION CRITERIA	METHOD OF ASCERTAINMENT
1. DSM-IV Axis 1 psychiatric diagnosis. Patients with Major Depressive Disorder will be eligible to participate, provided they are in remission (Hamilton Depression Scale Score < 8), whether receiving treatment or not.	MINI interview, self-report
2. Unstable physical disorders, which might make participation hazardous. Serum sodium (Na) < 133 mEq/L, renal failure (creat > 2, BUN > 40) is exclusionary. Patients on medications* (see partial list below) that may cause hyponatremia will not be excluded provided there is no evidence of hyponatremia at screening.	medical and physical examination
3. Diagnosis of Substance Abuse or Dependence disorder, with exception of nicotine dependence. Patients in remission may participate if its duration is greater than 2 years preceding participation.	Self-report, treatment history.
4. History of allergic, dermatological, or adverse event related to oxytocin or desmopressin. Patient using oxytocin or vasopressin-based products cannot participate.	Self-report, medical history.
5. Chronic organic mental disorder, insufficient proficiency in English that would render an individual incapable of giving informed consent.	Psychiatric evaluation
6. History of transphenoidal surgery, sinus surgery in the past month. Simple nasal congestion is not exclusionary.	History, medical screening.

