Control patients will participate only in phase 1. They will not be hospitalized, but the structure of the testing will be such as to reproduce the conditions under which the cocaine-dependent patients will be tested. When the two consecutive days of testing are completed, their participation ends. These will be matched for age and gender.

Phase 2 follows to study the effects of intranasal oxytocin on relapse risk to cocaine use after abstinence is induced. This phase of the study will be carried out identically at the STARS clinic, or at the Division on Substance Abuse at Albert Einstein College of Medicine. During this phase, patients must attend the clinic three times a week. At these visits, the randomized medication will be taken under supervision of research staff, from a bottle kept at the research site. On the days when the patient is not at the research site, the medication is taken as instructed from an at-home bottle. Compliance with at-home administration will be monitored by a single-blind weighing of the at-home bottle at each visit. At each visit, vital signs, adverse events, urine toxicology, and drug use are reviewed. At one visit, the patient will meet with a counselor for compliance enhancement therapy. At another visit, the patient will meet with a research MD for ratings, monitor progress, and review side-effects.

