- 2: On the days when patients do not attend the clinic, they will be asked to administer the randomized medication from an "at-home" bottle. They will be asked to bring the bottle at each visit to the clinic. In a single-blind fashion, it will be weighed as a measure of compliance. The metered bottle delivers 4 IU/0.1cc or per puff. Each daily dosing requires 6 puffs, or 0.6cc. The weight of each puff or 0.1 cc is approximately 0.1g. Hence, for each at-home insufflation, the bottle weight is expected to change by 600 mg. The expected change in weight will be plotted against the recorded change in weight, and this will be used to estimate at-home compliance.
- 3: At each visit, vital signs are recorded, and an inquiry is made about adverse events. The Time-Line-Follow-Back is completed to review drug use by calendar date. This allows a day-to-day review of reported drug use for each day of participation.
- 4: At week 2, 4, and 6, a thorough medical review will be carried out to ensure patient safety. This will include a review of systems, with a focus on lethargy, fatigue, nausea, and weakness, which are the usual symptoms of hyponatremia. Although the risk is remote, hyponatremia would be the major metabolic complication that could arise from intranasal oxytocin. Of note is the fact that it has been reported when oxytocin is used in the induction of labor with continuous intravenous infusion (Pitocin, PDR, 2014), a condition vastly different from those of this study. A blood draw will be done to monitor electrolytes and

---

blood counts. For women, a urine pregnancy test will also be done. Detection of pregnancy ends participation in the study.

5: Self-reports that will be completed weekly at one of the visits: Perceived Stress Scale, Cocaine Craving Scale.

6: The vital sign form, the review of system form (including blood results) will be dated and will refer to a calendar date of the clinical trial week it was performed to ensure proper recording.

7: At one of the visit, patients will meet with a research psychiatrist to review participation, whether progress or regress is being made, and to complete clinical ratings that will include a Substance Use Inventory, the Clinical Global Impression scale, a medical review, and completion of all clinical notes. All these forms are dated. These are then recorded in the clinical trial week form that corresponds to the calendar dates for that week.

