4. Oxytocin: Oxytocin is used during labor and delivery to promote uterine contraction. In this instance, doses vary, but far exceed the daily dose of 24 IU/day used in this study. Administered intravenously as Pitocin, it can also lead to hyponatremia, arrhythmia, convulsions, chest pain, shortness of breath, confusion, swelling, headache, nausea/vomiting, cardiac arrhythmia. During their participation, control participants will receive 2 consecutive doses of IN oxytocin (40 IU in total) during phase 1. Cocaine-dependent patients receive 47 doses of IN oxytocin (940 IU) over a period of 7 weeks. No serious adverse events arose in a study during which 40 IU were administered daily for one week, then 80IU/day for another 7 weeks (Modabbernia et al., 2013). Feeling too relaxed, light-headedness, anxiety, clouded thinking, and nasal cavity irritation are the most common side effects reported in protocols approximating the one presented here (Rodrigues et al., 2009; Ditzen et al., 2009).
  
5. Another potential risk, especially for intranasal cocaine users, is whether the use of the intranasal approach would serve as a trigger for cocaine use. As this pharmacological approach has not been investigated before, this will be specifically queried for during clinic-based administration.
  
6. No data exists examining the risk of cocaine use is enhanced by concomitant intake of oxytocin. We

---

do not anticipate that it would increase the risk of cocaine use. As change in cocaine use is a main outcome of the study, evidence of increased cocaine use will be monitored closely.

7. The stress challenge may cause patients to experience cravings for cocaine. After each procedure, a gradual muscle relaxation procedure will be used to reduce these.
  
8. Vouchers could be exchanged for drugs, or their monetary value could serve as a trigger to procure cocaine. Expending vouchers is a major topic of the counseling during the study to promote a drug-free lifestyle.
  
9. The structured interviews, self-reports, and questionnaires should not pose a physical risk. Their disadvantage is the time to complete them. Our past experience using these measures indicates that patients find them acceptable.
  
10. The risk of the blood tests is the discomfort associated with venipuncture, and a possibility of slight bruising. For the stress challenge, a saline lock will be placed to avoid repeated venipuncture.
  

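### The control exclusion list omits the pregnancy and breastfeeding criterion that applies to patients, although control women undergo the same phase 1 drug challenge

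*Protocol*

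**What the plan says.** The Protocol keeps separate eligibility tables for its two samples. In the cocaine-dependent table, exclusion 9 reads "Pregnancy, positive urine pregnancy test, or breastfeeding"; it also requires contraception and repeat pregnancy testing every two weeks of phase 2.

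The control table (Inclusion/Exclusion Criteria #2) has three inclusion and six exclusion criteria. The exclusions cover psychiatric diagnosis, unstable physical disorders, substance use disorders, previous reactions to or current use of the study peptides, inability to consent, and finally "History of transphenoidal surgery, sinus surgery in the past month. Simple nasal congestion is not exclusionary". Pregnancy, a pregnancy test and breastfeeding do not appear in either list.

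Under Recruitment Procedures, the medical evaluation includes a urine pregnancy test for women. Of the assembled results it says "This information is reviewed against the inclusion/exclusion criteria of the study to determine eligibility to participate", and it adds "For control participants, the screening process is the same as described for cocaine-dependent patients".

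The only rule that acts on a detected pregnancy after entry is "Detection of pregnancy ends participation in the study". It stands in Study Procedures, Phase 2, item 4. The Design Overview says of controls: "Control patients will participate only in phase 1".

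**The concern.** The reason for excluding pregnant or breastfeeding patients is exposure to desmopressin and oxytocin, and control women have that exposure too. The Risks section itself describes oxytocin as a drug used in labor to make the uterus contract. Controls are volunteers who are offered no treatment, so there is no therapeutic benefit to set against a risk to a pregnancy or a nursing infant.

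The eligibility table is what the reviewing physician is told to apply. If it is silent, a positive test in a control has no stated consequence, and a breastfeeding woman meets every written criterion. What is at stake is participant safety and consistent handling across the two sites. Power, the sample size and the planned comparisons are untouched.

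**Working it through.** No formula in the plan is in question. The check compares the two lists, looks for other text that might close the gap, and then sizes the exposure.

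**1. The lists side by side**

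| Topic | Patients | Controls |
|---|---|---|
| Unstable physical disorders | exclusion 5 | exclusion 2 |
| Reaction to, or use of, the study peptides | exclusion 2 | exclusion 4 |
| Pregnancy, positive test, breastfeeding | exclusion 9 | none |
| Recent nasal or sinus surgery | exclusion 10 | exclusion 6 |

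The control exclusions are numbered 1 to 6 without a gap, and the next section of the form follows directly. Nothing suggests that text was lost in extraction.

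**2. Are control women exposed?** Yes. The control sample is men and women aged 18 to 60 (Description of subject population), matched for age and gender (Design Overview), and put through the same challenge on two days (Phase 1, control participants).

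**3. Does other text supply the rule?**

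- *Control exclusion 2, unstable physical disorders.* It does not naturally cover a normal pregnancy or breastfeeding. The patient table has a matching criterion and still lists pregnancy separately.
- *The screening test.* Controls have it, but the results are judged against the listed criteria, and none of those for controls refers to it.
- *The phase 2 stopping rule.* It cannot reach someone who takes part only in phase 1.
- *Breastfeeding.* No test detects it, and no control criterion or procedure asks about it.
- *SAP.* Its pregnancy testing is part of phase 2 medical monitoring at weeks 2, 4 and 6, and so does not apply to controls.

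**4. Dose received by controls**

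- Desmopressin: 2 × 80 IU = 160 IU, against 3 × 80 IU = 240 IU for patients; 160/240 = 67%.
- Oxytocin, lower figure: the challenge procedure states "Then the patient is asked to insufflate 12 IU (16 ug or 0.3cc) of oxytocin in each nostril" on one day, so 2 × 12 IU = 24 IU.
- Oxytocin, upper figure: the Risks section states "control participants will receive 2 consecutive doses of IN oxytocin (40 IU in total) during phase 1".
- For comparison, the Risks section gives patients 47 doses and 940 IU, which is 47 × 20 IU. One dose in 47 is 2.1% (20/940, or 24/1,128 if each dose is 24 IU). The stated 40 IU is 40/940 = 4.3%. The 940 IU can apply only to patients randomized to oxytocin; placebo patients receive oxytocin only in the challenge.

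**5. Women to whom the control list applies.** Assume the 45% women expected under Gender and Ethnic Breakdown:

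- completers: 0.45 × 50 = 22.5, about 22 to 23;
- enrolled: 0.45 × 75 = 33.75, about 34.

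These counts describe the group the list covers, not the number at risk. The age range runs to 60, and the documents give no rate of pregnancy or breastfeeding.

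**The case against.** The strongest reply is that the gap is already largely handled. Recruitment Procedures describes the screening as a way of ruling out conditions that would make taking part hazardous, and applies the same screening to controls. The section on minimizing risks lists the urine pregnancy test within a baseline evaluation meant to detect unstable medical conditions. A physician who orders that test and sees a positive result would probably not enrol the woman. This reply has force for pregnancy: it would be wrong to say that the Protocol welcomes pregnant controls or leaves them untested. But those passages state a general purpose, not a criterion, and pregnancy is not obviously an unstable condition. For breastfeeding they help little.

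It can also be said that the hazard is modest. The Risks section notes that doses used in labor are much larger than 24 IU a day, and it describes an intravenous product. Control exposure is two testing days, and the documents quantify no uterine or infant risk from a brief intranasal dose. That is fair, and it limits the weight of the point. It does not explain why the same challenge calls for the exclusion in patients but not in controls.

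Finally, the control consent form and the separate screening protocol (IRB# 4436R) are not available and may contain pregnancy wording. That possibility stands. If they do, the eligibility table should still agree with them.

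**Conclusion.** The concern holds. The pregnancy and breastfeeding exclusion is absent from the control criteria, and control women receive both study peptides in the same challenge. Read literally, the list would admit a breastfeeding control and contains no criterion by which to exclude a pregnant one, even though she would be tested.

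The practical size is small. Exposure is limited to two days, and the women actually affected would be far fewer than the 22 to 34 covered by the list, a range that itself assumes controls mirror the expected 45% women. The conclusion that the criterion is missing rests on the eligibility tables alone and is secure. Whether such women are protected by documents not available here cannot be determined. No estimate, test or power figure changes. The point should be fixed because it concerns participant safety, the documents give no reason for the difference, and the remedy is nearly free.

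**What to change.** Add a seventh item to the control exclusion table that carries over the patients' wording: "Pregnancy, positive urine pregnancy test, or breastfeeding". Give the method of ascertainment as history plus the urine pregnancy test already done at screening. The repeat testing attached to the patient criterion belongs to phase 2 and need not be copied. Check that the control consent form and the screening protocol say the same.

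The cost is one line in the table and one history question on breastfeeding. No new laboratory test is needed, and the sample size and analysis do not change.
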